7.3 Subject Characteristics

Demographic information (e.g., age, race, height, weight, and body mass index) will be summarized using descriptive statistics.

Concurrent medications will be recorded and coded using a standard classification system.

Disease factors for subjects accrued to the study will be characterized using descriptive statistics.

7.4 Replacement Policy

Patients may be replaced for the following reasons:

- Inability to tolerate/complete baseline PET
- Sub-optimal timing of post-injection PET scan compromising ability to detect metastatic lesions

7.5 Accrual estimates

The estimated accrual period is approximately 36 months.

7.6 Interim Analysis

An interim analysis for safety will be performed after 6 patients have enrolled to Cohort A. If more than 33% of patients experience a Grade ≥ 2 related adverse event, study accrual will be halted and alternative dose levels may be explored.

An informal analysis to confirm feasibility will be performed after approximately 6 patients are enrolled on Cohort A. Images will be qualitatively reviewed and preliminary data with respect to signal-to-noise ratio within metastatic lesions will be assessed by body site. If it is determined that insufficient signal- to-noise ratio is present, additional patients may be accrued in Cohort A with proper technological adjustments (e.g. timing of post-injection scan acquisition, injected dose of radiotracer) to ensure optimal intra-tumoral uptake of tracer before proceeding to Cohort B and C enrollment.

7.7 Analytic Plan

7.7.1 Analysis Population

All data from all subjects dosed in the study will be included in all listings, plots, summary tables, and statistical analyses when appropriate. Missing values will not be substituted by estimated values, but treated as missing in the statistical evaluation.

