Appreciating these concerns, several years ago we began developing small molecule radiotracers for PET to identify Enz resistant CRPC lesions that express GR. Our interest in this area stemmed from early preclinical reports showing that GR overexpression in human prostate cancer xenografts was a spontaneous response to chronic Enz treatment, and GR transcriptional activity overcame the antitumor effects of Enz therapy in vitro and in vivo (**Figure 1A**). Since this milestone, numerous manuscripts from other labs have disclosed biological findings supportive and consistent with these data. Moreover, preclinical studies have shown that dual AR/GR antagonists, or selective GR antagonists paired with Enz have antitumor activity (**Figure 1B**). Collectively, these data strongly support a role for GR expression and biology in resistance to anti-androgen therapy, and three ongoing clinical trials are testing the therapeutic potential of overcoming treatment resistant CRPC with GR antagonists more systematically (CORT125281: NCT03437941; ORIC-101: NCT03928314; RU486: NCT02012296).

With the current enthusiasm for GR as a drug target, the timing is ideal to conduct human imaging studies to determine if GR expression in mCRPC can be visualized on PET. Achieving

this goal would empower the community with a crucial companion diagnostic for (1) prospectively identifying patients whose tumors express GR to evade Enz (and therefore may be likely to respond to a GR antagonist), and (2) studying the PD effects of GR antagonists holistically to identify dosing strategies that maximize antitumor effects while minimizing on-target, off tissue effects.

Our studies identified a small molecule radiotracer, termed ^{11}C -YJH08 that specifically binds to GR in rodent models, and has excellent pharmacokinetic properties (**Figure 1B**).

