7.7.3 Analysis of Secondary and Exploratory Endpoints

The frequency and severity of adverse events following ^{11}C -YJH08 injection will be descriptively reported, using CTCAE v 5.0. Organ dosimetry on PET will be calculated using standard technique.

The median and range for intra-tumoral SUV_{max} within metastatic lesions will be descriptively reported to asses for intra-tumoral heterogeneity and differences in uptake by site of disease.

For the purposes of analyzing the association between baseline and percent change from baseline in $\text{SUV}_{\text{max-ave}}$ with subsequent clinical outcomes, the cohort will be dichotomized above and below the median for the study cohort. The PSA response rate (PCWG3 criteria; Cohort B only), clinical benefit rate, and objective response rate (in subset of measurable tumors by RECIST 1.1) will be compared between dichotomized groups using the chi-squared test. The

log rank test will be used to compare progression-free survival between dichotomized subgroups.

For patients who undergo optional tumor biopsy with evaluable tumor content, the correlation between SUV_{max} of the target lesion on PET with GR expression by IHC (using H-score method) will be computed using Pearson correlation method. Likewise, the correlation between SUV_{max} on PET with GR transcriptional signature activity by RNA-seq will be determined using Pearson correlation method when sufficient tumor content permits transcriptional analysis.

No adjustment will be made for multiple comparisons for the analysis of the secondary and exploratory endpoints.

8 Study Management

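### Read literally, the missing-data rule in 7.7.1 drops Cohort B/C patients with no post-baseline assessment from the response rates in 7.7.3, even when the cause is death or early treatment failure

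*Combined protocol and SAP*

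**What the plan says.** Section 7.7.1 (Analysis Population) has two sentences. The first sets the population: "All data from all subjects dosed in the study will be included in all listings, plots, summary tables, and statistical analyses when appropriate". The second is the only missing-data rule in the plan: "Missing values will not be substituted by estimated values, but treated as missing in the statistical evaluation".

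Section 7.7.3 addresses secondary objective 3, the link between uptake and later outcome in Cohorts B and C. For the grouping, "the cohort will be dichotomized above and below the median for the study cohort". PSA response, clinical benefit and objective response "will be compared between dichotomized groups using the chi-squared test". Only two denominator restrictions appear: Cohort B for PSA response, and for objective response "in subset of measurable tumors by RECIST 1.1".

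Neither section says how to class a patient who has no post-baseline assessment. The plan defines no response-evaluable set, no non-responder rule and no sensitivity analysis. The replacement policy (7.4) covers an incomplete baseline PET and poor scan timing only. The schedule table after 5.2.3 marks PSA and staging scans at screening only.

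**The concern.** A patient who dies or fails clinically before any follow-up scan or PSA has no recorded response value. Applied as written, the 7.7.1 rule leaves that value missing, and the patient drops out of both numerator and denominator. Yet the reason the value is missing tells us the treatment did not work. Removing such patients raises the response rate of whichever group they belong to.

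The comparison by uptake is then exposed. Section 1.1 motivates the tracer with the finding that "GR transcriptional activity overcame the antitumor effects of Enz therapy in vitro and in vivo". If that carries over to Cohort B, high-uptake patients would fail early more often, and dropping them would hide the association that objective 3 looks for. Missing assessments are plausible: the patients have metastatic disease, Cohort B enters after progression, and no protocol visit secures a post-baseline scan or PSA.

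**Working it through.** **Inputs from the documents.** Section 7.2 plans 10 evaluable patients per cohort, with a 20% inevaluable rate and 12 recruited. A median split of 10 gives about 5 v 5, reading the split as made within each cohort. The objective-response subset may be smaller.

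**The plan's own figure.** The 12 reproduces as 10 × 1.20 = 12; dividing instead gives 10 / 0.80 = 12.5, rounded up to 13. The plan states no alpha, power or effect size for the response comparison, so nothing else can be reproduced.

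**Assumed inputs.** The documents give neither response rates nor the share unassessed by uptake group. The values below are illustrative, and all unassessed patients are taken to be failures.

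**Formula.** Let p be the true response rate with every qualifying patient counted, and m the share unassessed. The complete-case rate is p / (1 − m).

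**Groups of five, with failures dropped from the high-uptake group only:**

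| All counted (low v high) | Dropped | Complete case (low v high) | Low minus high, in points |
|---|---|---|---|
| 2/5 v 2/5 (40% v 40%) | 1 | 2/5 v 2/4 (40% v 50%) | 0 becomes −10 |
| 2/5 v 2/5 (40% v 40%) | 2 | 2/5 v 2/3 (40% v 67%) | 0 becomes −27 |
| 2/5 v 1/5 (40% v 20%) | 1 | 2/5 v 1/4 (40% v 25%) | 20 becomes 15 |
| 2/5 v 1/5 (40% v 20%) | 2 | 2/5 v 1/3 (40% v 33%) | 20 becomes 7 |

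The spurious 27-point gap has p = 0.47 by chi-squared test without continuity correction. The harm is to the estimate, not a false significant result.

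**Expected rates, with true response 30% (high) v 50% (low), a 20-point gap:**

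| Unassessed (high v low) | Complete case (high v low) | Gap, in points |
|---|---|---|
| 30% v 10% | 0.30/0.70 = 43% v 0.50/0.90 = 56% | 13 |
| 40% v 10% | 0.30/0.60 = 50% v 0.50/0.90 = 56% | 6 |
| 40% v 0% | 0.30/0.60 = 50% v 50% | 0 |
| 20% v 20% | 0.30/0.80 = 37.5% v 0.50/0.80 = 62.5% | 25 |
| 10% v 30% | 0.30/0.90 = 33% v 0.50/0.70 = 71% | 38 |

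More missingness among high-uptake patients shrinks the gap. Equal missingness widens the difference and leaves the ratio unchanged. More missingness among low-uptake patients widens the gap further. With equal true rates and equal missingness (40% v 40%, 20% unassessed in each group), both rates rise to 50% and the difference stays 0.

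**The case against.** The strongest reply is that the plan never says these patients are excluded. Section 7.7.1 bars substituting estimated values. Classing a known early death as a non-responder defines the endpoint and estimates nothing, and the same section includes all dosed subjects where appropriate. Section 7.7.3 also names PCWG3 and RECIST 1.1, and how those criteria class unassessed patients cannot be checked from these documents. This stands as far as it goes: there is no express exclusion. But the plan never makes the non-responder classification, its one stated rule points the other way, and an open denominator could be settled after the data are seen.

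Four stronger readings are tempting, and the documents do not support them.

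- **That every treatment failure is lost.** Documented progression is an observed outcome. Only patients with no post-baseline scan or PSA are affected.
- **That the rule necessarily works against the hypothesis.** The direction depends on missingness rates that the plan does not give. The Section 1.1 rationale concerns enzalutamide and prostate cancer models. It does not cover Cohort C, and the therapy after baseline is not fixed in either cohort.
- **That the association would be reversed.** From 30% v 50%, reversal needs more than 40% of high-uptake patients unassessed even with none in the low-uptake group. Small counts can be chosen to produce it: 3/5 (low) v 2/5 (high) becomes 60% v 67% if two high-uptake failures are dropped. Nothing in the documents supports such inputs.
- **That PFS counts the same patients as events, so the two analyses conflict.** Section 7.7.3 names only the log rank test and defines neither events nor censoring.

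It is also fair to say that the stakes are modest. The cohorts are convenience samples sized for lesion-detection sensitivity, no adjustment is made for multiple comparisons, and neither a primary endpoint nor the decision to open Cohorts B and C uses these rates.

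**Conclusion.** The point holds in limited form. Applied literally, the single rule in 7.7.1 removes patients with no post-baseline assessment from three response rates, including patients known to have failed. Rates are then inflated, and the comparison by uptake can be distorted in either direction. At about 5 v 5, one or two such patients move a group's rate from 40% to 50% or 67%, which is 10 to 27 points. If early failures concentrate in high-uptake patients, the association moves toward zero. That is a conditional statement resting on the Cohort B rationale. The response rates and missing shares are assumptions throughout. This is a low-severity matter in an unpowered secondary analysis: a cheap improvement.

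**What to change.** Add an exception in 7.7.1 and 7.7.3 for the response endpoints:

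1. The denominator is every patient with a baseline PET who qualifies for the endpoint: measurable disease for objective response, Cohort B for PSA response.
2. Patients with no post-baseline assessment because of death, progression or stopping therapy count as non-responders.
3. The number unassessed is reported by uptake group, with reasons. Patients lost for other reasons are shown too.
4. The complete-case result is given as a sensitivity analysis.

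The cost is a few sentences in the plan, slightly lower reported response rates, and recording why an assessment is missing. The last item needs a place on the case report form, because the schedule table shows no post-baseline PSA or staging scan and no collection of these reasons.

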7.7.2 Primary Analysis

For Cohort A, Using as a cut-off to define a positive lesion on PET as a lesion with SUV at least 1.5 times higher than mediastinal blood pool, the sensitivity of ^{11}C -YJH08 PET will be descriptively reported on a lesion-per-lesion basis, using as reference standard staging scans including CT or MRI of the chest/abdomen/pelvis.

For Cohorts B and C, the median percent change from baseline, and range of SUV_{max} (across all metastatic lesions per patient) and $\text{SUV}_{\text{max-ave}}$ (in each study cohort) will be descriptively reported using mediastinal blood pool and normal organ as background uptake values. Wilcoxon signed rank test will be used to compare the follow up to baseline PET scan values at lesion level and patient level.

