Investigational Medicinal Product	¹¹ C-YJH08 at a dose of up to 20 mCi will be administered. It will be injected intravenously. For cohort A (n = 6), dosimetry calculation will be performed by obtaining whole body (vertex to thighs) PET images up to five time points during 0-90 minutes post injections. For cohort B and C (n=10 each), one time point will be obtained based on the results of cohort A.
Study population	Approximately 26 patients total will be enrolled in one of two following cohorts: Cohort A (N = 6 patients): Patients with any solid tumor malignancy with evidence of one or metastases on conventional imaging. Cohort B (N = 10 patients): Patients with metastatic CRPC will undergo ¹¹ C-YJH08 PET at the time of progression by PCWG3 criteria on systemic therapies (e.g. enzalutamide, apalutamide or darolutamide). Cohort C (N = 10 patients): Patients with any solid tumor malignancies other than prostate adenocarcinoma with one or more metastases on conventional imaging. Enrollment in Cohort B and C will be conducted after completion of enrollment in Cohort A.
Rationale for Study	The proposed patient studies represent the first-ever cancer patient imaging studies with ¹¹ C-YJH08 PET. The patient population for Cohort A is designed to determine the dosimetry of the imaging agent, and will enroll any solid tumor malignancy. The patient population for Cohort B is designed to enrich for GR-overexpressing tumors, by selecting mCRPC patients at the time of progression by PCWG criteria on systemic therapies. And Cohort C is designed to include patients with any solid tumor malignancies other than prostate adenocarcinoma with one or more metastases on conventional imaging. Successful completion of the dosimetry cohort (Cohort A) will provide the necessary preliminary data to support subsequent enrollment in Cohort B and C.
Primary Objectives	
 1. Cohort A: To determine the feasibility of metastatic lesion detection in using ¹¹C-YJH08 PET. 2. Cohort B and C: To determine the mean percent change from baseline at the time of progression on systemic therapy in $SUV_{max-ave}$ on paired ¹¹C-YJH08 PET on a per-patient and per-lesion basis.

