2.2 Primary Objectives

Primary Objective	Endpoint(s)	Time Frame
1. Cohort A: To determine the feasibility of metastatic lesion detection in using ^{11}C -YJH08 PET.	Cohort A: Sensitivity of metastatic lesion detection in using ^{11}C -YJH08 PET.	2 days
2. Cohort B and C: To determine the mean percent change from baseline at the time of progression on systemic therapy in $\text{SUV}_{\text{max-ave}}$ on paired ^{11}C -YJH08 PET on a per-patient and per-lesion basis.	Cohort B and C: Mean percent change from baseline at the time of progression on systemic therapy in $\text{SUV}_{\text{max-ave}}$ on paired ^{11}C -YJH08 PET on a per-patient and per-lesion basis.	Baseline to time of progression

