3.3.1 Inclusion Criteria

Subjects may be included in the study if they meet all of the following criteria:

1. Disease characteristics by cohort, as defined by:

Cohort A) Histologically-confirmed metastatic solid tumor malignancy.

Cohort B) Metastatic castration-resistant prostate cancer with progression on systemic therapies by PCWG3 criteria.

Cohort C) Metastatic advanced solid tumor malignancy other than prostate adenocarcinoma with at least one metastasis on conventional imaging.

2. The subject is able and willing to comply with study procedures and provide signed and dated informed consent.
3. Eastern Cooperative Oncology Group (ECOG) Performance Status of 0 or 1.
4. Age 18 years or older at the time of study entry
5. Adequate organ function, as defined by:
 - Serum creatinine \leq 1.5 x ULN OR estimated creatinine clearance $>$ 50 ml/min
 - Total bilirubin \leq 1.5 x ULN
 - Hemoglobin \geq 8.0 g/dL
 - Platelet count \geq 50,000/microliter
 - Absolute neutrophil count \geq 1000/microliter

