5.2.3 OPTIONAL ^{11}C -YJH08 PET at Progression (Cohorts B and C)

Patients will undergo optional repeat ^{11}C -YJH08 PET at the time of progression by PCWG3 criteria for Cohort B and RECIST 1.1 criteria for Cohort C. Patients who underwent PET/CT at baseline should have same imaging modality performed during follow-up, and likewise patients who underwent PET/MR at baseline should have same imaging modality performed during follow up.

- Vital Signs
- Concomitant medication review

Period/ Procedure	Screening (Day -28 thru C1D1)	Cycle 1, Day 1 (Baseline PET)	Disease Progression (Cohort B and C)
Study / Investigational Product Administration			
¹¹ C-YJH08 PET		X	X
Administrative Procedures			
Informed consent	X		
Clinical Assessments			
Baseline conditions	X		
Vital signs ¹	X	X	X
Concomitant medications	X		X
AE assessment ²	X	X	
Demographics	X		
Performance status	X		
Laboratory Assessments			
Serum creatinine, total bilirubin, AST, ALT, CBC + diff ³	X	X	
PSA, Serum Testosterone	X		
Imaging Procedures			
Staging scans (CT or MRI)	X		
ECG/EKG		X ⁴	
Tissue Collection/ Biopsy			
Tumor biopsy (optional) ⁵		X	

¹ Vital signs (blood pressure, heart rate) will be collected at screening, before and after administration of ¹¹C-YJH08 injection, then at 60 minutes (+/- 15 min), and 2 hours (+/- 30 min) following ¹¹C-YJH08 injection.

² Safety monitoring will include adverse event assessment at screening, 60 minutes (+/- 15 min), 2 hours (+/- 30 min) and 24 hours (+/- 4 hours) following ¹¹C-YJH08 injection.

³ Serum creatinine, total bilirubin, AST, ALT, and CBC + diff will be performed at screening and at 24 hours (+/- 4 hours) following ¹¹C-YJH08 injection.

⁴ EKG will be performed prior to ¹¹C-YJH08 injection and at 2 hours (+/- 30 min) following ¹¹C-YJH08 injection.

⁵ Metastatic tumor biopsy is optional. Tumor biopsy should be performed within 14 days following baseline PET. Soft tissue, PET-avid lesions should be prioritized for biopsy whenever feasible.

Supportive Care

Subjects will receive full supportive care as medically indicated.

The Principal Investigator or designee will be present during the administration and monitoring period. Any events occurring during or subsequent to the administration of IMP will be addressed as required by the monitoring nurse and/or physician as deemed appropriate.

6 Reporting and Documentation of Results

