7.1 Imaging Analysis

A trained nuclear medicine physician will evaluate the reconstructed PET, CT or MRI, and fused PET/CT or PET/MR images using a PET volume computer-assisted reading software package. A positive lesion on PET will be defined as a focus of activity with at least 1.5 times higher SUV compared with mediastinal blood pool that is not attributable to other etiologies of tracer distribution (e.g. inflammation, excretion). A volume of interest (VOI) will be semiautomatically placed around each lesion, and the calculated maximum standard uptake value (SUV_{max}) will be recorded for each lesion, including lesions that are detected on standard scans but are not positive on PET. Adjusted SUV_{max} data will then be averaged across all lesions within a given patient ($SUV_{max-avg}$). In order to avoid clustering effects, analysis will be limited to the five largest osseous metastases and all visceral/soft tissue metastases.

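### The Cohort B/C lesion-level signed-rank test ignores within-patient correlation; the lesion limit in 7.1 reduces that correlation's effect without removing it, so the lesion-level primary p-value can be too small

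*Combined protocol and SAP*

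**What the plan says.** Section 2.2 defines the Cohort B/C primary endpoint as change in SUVmax-ave between paired scans, "on a per-patient and per-lesion basis". Lesion level is therefore part of the primary endpoint.

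Section 7.7.2 gives the test: "Wilcoxon signed rank test will be used to compare the follow up to baseline PET scan values at lesion level and patient level". No clustered rank test, mixed model or resampling by patient is named anywhere, and no alpha is stated.

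Section 7.1 contains the only provision for clustering: "In order to avoid clustering effects, analysis will be limited to the five largest osseous metastases and all visceral/soft tissue metastases".

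The second scan is not mandatory. Section 5.2.3 reads: "Patients will undergo optional repeat ^{11}C -YJH08 PET at the time of progression by PCWG3 criteria for Cohort B", with RECIST 1.1 used for Cohort C. Section 7.2 aims for 10 evaluable patients per cohort.

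On the summary measure, section 2.2 names the "mean percent change from baseline at the time of progression on systemic therapy in" SUVmax-ave, and the abstract agrees. Section 7.7.2 instead has "For Cohorts B and C, the median percent change from baseline".

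**The concern.** The ordinary signed-rank test gets its null distribution by treating the sign of each difference as an independent coin toss. Lesions in one patient share the systemic therapy, the same two tracer injections and the same blood-pool reference, so their changes are likely to move together. Pooling them overstates the amount of independent information and makes the p-value too small.

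The limit in 7.1 reduces the number of bone lesions per patient. It cannot make the remaining lesions independent, and it leaves visceral and soft-tissue lesions uncapped. Lesion counts may be very unequal, particularly in Cohort C, where entry requires only "Metastatic advanced solid tumor malignancy other than prostate adenocarcinoma with at least one metastasis on conventional imaging". One patient with many lesions could then dominate the pooled test.

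Neither test is given priority. If few patients return for the optional scan, the lesion-level result may be the only nominally significant one, and it is the one with the wrong size. The mean/median mismatch is a separate problem: the headline figure could be chosen after the data are seen.

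**Working it through.** **The plan's own figure.** The documents give no alpha, power or effect size for this test, so there is no operating characteristic to reproduce. The only related figure is the recruitment target in 7.2: 10 × (1 + 0.20) = 12 patients per cohort. At a 20% inevaluable rate, 12 × 0.8 = 9.6 evaluable are expected. Uptake of the optional repeat scan is not stated. A declined progression scan is not among the replacement grounds in 7.4, so fewer than 10 pairs is plausible.

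**Assumptions not in the documents.** Two-sided 5% level; lesions per patient (m); ICC of lesion changes; and, in the last two table rows, the number of pairs.

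**Approximation.** With equal lesion counts the design effect is DE = 1 + (m − 1) × ICC, and the actual type I error is about 2 × [1 − Φ(1.96/√DE)]. For m = 5 and ICC 0.3, DE = 1 + 4 × 0.3 = 2.2, 1.96/√2.2 = 1.32, and the error is about 0.186.

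**Simulation.** Exact signed-rank test, normal patient effect plus normal lesion effect, no true change. There were 20,000 runs per setting for equal counts with 10 patients, and 40,000 for the other rows. Entries are the rejection rates of the lesion-level test.

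| Paired patients and lesions | ICC 0.1 | ICC 0.3 | ICC 0.5 |
|---|---|---|---|
| 10 patients, 2 each | 0.061 | 0.082 | 0.104 |
| 10 patients, 3 each | 0.071 | 0.114 | 0.162 |
| 10 patients, 5 each | 0.095 | 0.179 | 0.251 |
| 10 patients, one with 14, nine with 4 (50 lesions) | 0.119 | 0.232 | 0.330 |
| 10 patients, one with 23, nine with 3 (50 lesions) | 0.172 | 0.361 | 0.491 |
| 6 patients, 5 each | 0.095 | 0.185 | 0.259 |
| 5 patients, 5 each | 0.093 | 0.182 | 0.259 |

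With 10 patients and 1 lesion each the rate is 0.051, so the test is sound when independence holds. At ICC 0.7 it is 0.317 with 5 lesions and 0.475 with 10. A second simulation using the normal approximation to the test gave 0.183 and 0.249 for 10 patients with 5 lesions at ICC 0.3 and 0.5, in agreement with the table.

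**What the 7.1 limit achieves.** At ICC 0.3 with 10 patients:
- 15 lesions each, no limit: 0.390
- exactly 5 each: 0.178
- 5 bone lesions plus 0-12 soft-tissue lesions each (77 in total): 0.294

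At ICC 0.5 these are 0.488, 0.256 and 0.391. The limit lowers the inflation and leaves a large part of it.

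**Patient-level test.** With 10 pairs its size is 0.047-0.053. With 6 pairs it is 0.031-0.033. The smallest exact two-sided p with n pairs is 2/2ⁿ: 2/2⁵ = 0.0625 for 5 pairs and 2/2⁶ = 0.031 for 6. With 5 pairs only the lesion-level test can fall below 0.05.

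**The case against.** The strongest reply concerns weight. This is a first-in-human phase 1 study with convenience samples. The stated Cohort B/C hypothesis (2.1) and the sample-size rationale (7.2) concern detection sensitivity, not change in uptake. Section 7.7.2 presents the change descriptively, attaches no alpha or decision rule, and pre-specifies a valid patient-level test in the same sentence. All of this is true, and it is why no trial decision is at risk. It does not make the lesion-level p-value correct. The plan places that test under its primary analysis, and with 10 patients, 5 lesions each and ICC 0.3, about 14% of null trials would give a significant lesion-level result beside a non-significant patient-level one.

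The size of the error is also uncertain. If Cohort C patients mostly have one or a few lesions, the inflation is modest: five patients with 1 lesion and five with 3 give 6.5%, 9.6% and 13.6% at ICC 0.1, 0.3 and 0.5. SUV is already normalised for injected activity, and the adjustment for background may remove some shared variation, although a noisy common reference could add some. High ICCs are therefore not established. These points stand, and they are why the result is given as a range that starts near 5%.

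Finally, demoting the lesion-level test could be called a reviewer's preference, since 2.2 names both levels. That is fair so far as it goes; a cluster-aware lesion-level test is an acceptable alternative.

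**Conclusion.** The concern holds. The problem and its direction follow from the documents; its size depends on the assumed alpha, ICC, lesion counts and number of pairs. For 10 paired patients with equal counts and ICC 0.1-0.5, the nominal 5% test has a type I error of 6-10% with 2 lesions each, 7-16% with 3 and about 10-25% with 5. Concentrating the same 50 lesions in one patient raises the range to 12-33% (14 lesions) or 17-49% (23 lesions). The inflation is no smaller with fewer pairs: 9-26% with 5 or 6 patients and 5 lesions each, against 0% and about 3% for the patient-level test. With zero correlation, or one lesion per patient, there is no inflation.

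The mean/median conflict between the abstract and 2.2 on one side and 7.7.2 on the other is plain in the text and needs no calculation.

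Both should be fixed before Cohort B/C data are analysed. Neither affects a go/no-go decision.

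**What to change.** 1. **7.7.2.** Make the patient-level signed-rank test the only inferential primary test. State that with fewer than 6 paired patients it cannot reach two-sided 0.05, and that results are then descriptive only. Report lesion-level change descriptively.
2. **If a lesion-level test is wanted**, use a cluster-aware method with small-sample control. One option is a random-patient-intercept model (REML) on log(follow-up/baseline SUVmax), with a t reference on (paired patients − 1) degrees of freedom. Its simulated size was 0.026-0.057 with 6 and 10 patients, equal and unequal counts, and ICC 0.1-0.5. The same model with a normal reference gave 0.065-0.116, and a percentile bootstrap by patient gave 0.096-0.155, so neither should be used. To stay with rank tests, flip the signs of whole patients on the lesion signed ranks: size 0.049 and 0.052 at ICC 0.3 and 0.5 with 10 patients and 5 lesions each. With 5 pairs this test cannot reach 0.05 either.
3. **7.1.** Say that the lesion limit reduces clustering and does not remove it.
4. **Abstract, 2.2 and 7.7.2.** Name one summary as primary throughout, for example the median, which 7.7.2 already reports beside a rank test.

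The cost is wording in four places and a few lines of code, with no new patients, scans or data. Lesion-level evidence will look weaker, or its intervals will be wider.
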